7. SPECIFIC METHODOLOGY

7.1 Behavioral and cognitive impairment scales and tests

The cognitive measurement instruments used are mainly those sensitive to change, in regard to the nature of the study (pre-post condition). Specifically, the following tests are will be performed (see **Appendix 7**):

7.1.1 *Gold standards for the study of dementia*

Screening: Mini-Mental Status Examination (MMSE)³⁶. This test is widely used to assess cognitive alterations, and is the most commonly used brief screening test. The score ranges from 0 to 30, and is obtained by summing the points corresponding to each answer. Results below 26 points may indicate cognitive impairment. The test performed on occasion of the selection visit will serve as criterion for inclusion in the study. The subject is required to yield a score of ≥ 18 and ≤ 26 points.

For the evaluation of cognitive function in AD: Alzheimer's Disease Assessment Scale-Cognitive (ADAS-Cog)³⁷. This is an instrument specifically designed to evaluate the severity of the fundamental alterations in cognitive and behavioral function that are characteristic of patients with AD. The instrument consists of two parts (ADAS-Cog and ADAS-no Cog): the first measures cognitive function and the second (not to be applied in the present study) assesses non-cognitive (behavioral) function. The first part comprises 11 subtests that explore different areas: spoken language skills, test instructions recall, difficulty finding words, following instructions, naming objects, construction of figures, ideation praxis, orientation, recall and recognition of words. Scoring is by errors, and the total score ranges from 0 (no impairment) to 70 (maximum impairment).

7.1.2 *Specific neuropsychological battery (NPS battery)*

a) **Processing speed**

- i. *Symbol Digit Modalities Test (SDMT)*³⁸: developed principally for examining visual attention and tracking, concentration and psychomotor speed. The correct symbol-number pairs during 90 seconds are counted. Maximum score = 110.
- b) **Language (global measures)**
 - i. *Semantic and phonetic verbal fluency (animals per minute)*^{39,40}: allowing voluntary access to a certain vocabulary assessing reduction in verbal spontaneity and fluency difficulties.
 - ii. *Boston Naming Test (BNT)*⁴¹ *reduced to 15 words*: This is an essential test for the assessment of semantic memory in dementia evaluation protocols. The total score is the sum of the correct answers given spontaneously, together with the correct answers after a semantic cue. The first incorrect item is also reflected in the last section.
- c) **Verbal memory (immediate/delayed)** - *Rey Auditory Verbal Learning Test (RAVLT)*⁴²: This is a test of 5 learning series of 15 words presented in the same order that the subject listens and must remember and repeat at the end of each series. Next, a new series of 15 different words is administered as interference. Again, the subject is asked to remember the initial series. Finally, after 30 minutes, the subject is asked to the words from the initial list (deferred memory). Scoring is based on the number of words recognized.

In addition, the following instruments are included for the measurement of other variables:

Functional ability

*Activities of daily living: Alzheimer's Disease Cooperative Study - Activities of Daily Living (ADCS-ADL)*⁴³: This offers detailed descriptions of each activity and requests the informer to describe the actions or behaviors observed. The evaluator describes ability to carry out a series of activities of daily life (e.g., personal hygiene, using the phone, leaving home, etc.). The total sum is not calculated, though increased autonomy is associated with higher scores.

Neuropsychiatric disorders

*Neuropsychiatric Inventory (NPI)*⁴⁴: This evaluates the most frequent neuropsychiatric manifestations of dementia and also determines their frequency and intensity. Generally, the NPI is used to evaluate the changes in patient behavior that have appeared in the course of a given period of time. The NPI comprises 12 domains: delusions, hallucinations, dysphoria, apathy, euphoria, disinhibition, aggressivity and restlessness, irritability, anxiety, aberrant motor behavior, appetite and eating disorders, and nocturnal behavior. Each domain comprises an exploratory question, where an affirmative answer is followed by a series of seven to nine follow-up questions relating to symptoms present or not in that particular domain.

Frequency is scored as follows: 0 = none; 1 = occasional [less than once a week]; 2 = often [more or less once a week]; 3 = frequent [several times a week]; 4 = very frequent [daily or continuously].

Severity is scored as 1 = mild; 2 = moderate [if possible to reconduct by care taker]; 3 = severe [if not possible to reconduct].

The NPI thus evaluates response to therapy; the total score of the NPI is obtained by adding the scores (frequency x severity) of all the inventory domains. The score on the stress scale is not included in the total NPI score.

Measurement of depression in dementia: Cornell Scale for Depression in Dementia (CSDD)⁴⁵. This scale evaluates the signs and symptoms of major depression in patients with dementia. The information is obtained from two semistructured interviews - one with the caretaker and the other with the patient. Each item is scored for intensity (0 = none; 1 = mild or intermittent; 2 = severe).

Clinical grading of dementia, global evolution: Clinical Dementia Rating – Sum of boxes (CDR-Sb)^{46,47}. This is a clinical test validated in patients with AD. Impairment is scored as follows: 0 = normal; 0.5 = slight cognitive impairment or questionable dementia; 1 = slight dementia; 2 = moderate dementia; 3 = severe dementia. Six categories are contemplated: memory, orientation, judgment and problem solving, social and occupational activities, domestic activities and hobbies, and personal care.

Clinical global impression of change: Alzheimer’s Disease Cooperative Study – Clinical Global Impression of Change (ADCS-CGIC)⁴⁸. This instrument offers a method for the reliable assessment of global change in a clinical trial from baseline, using a 7-point Likert scale. It is administered to the caretaker and to the patient.

7.2 Method of Behavioral and Cognitive Testing

The established order in each visit will be as follows:

With the patient:

Rater 1

- a) MMSE (when stated by the protocol)
- b) ADAS-Cog
- c) NPS battery
 - i. RAVLT (Parts 1, 2, 3, 4 and 5)
 - ii. RAVLT (Part 6: interference)
 - iii. RAVLT (Part 6B: evocation)
 - iv. BNT (15 items)
 - v. SDMT
 - vi. Semantic and phonetic verbal fluency
 - vii. CSDD (includes the 30 minutes for differed memory)
 - viii. RAVLT (Part 7: differed memory 30 minutes after part 6B)
 - ix. RAVLT (Part 8: differed recognition)
- d) QoL-AD
- e) C-SSR (only once rater 1 has administered scales to caretaker)

Rater 2

Next, the global impairment and clinical impression scales are administered by the second evaluator:

- a) CDR-Sb
- b) ADCS-CGIC

With the care taker:

The second evaluator, while the evaluator 1 is administering the above mentioned battery, will administer the global impairment and clinical impression scale to the care taker in the following order:

- a) CDR-Sb
- b) ADCS-CGIC

The first evaluator, once he has finished the NPS battery, will interview the care taker to evaluate the subject functionality and behavior:

- NPI
- ADCS-ADL
- CSDD
- QoL-AD
- RUD-Lite

Evaluators are blinded to patient treatment. Importantly, the evaluators of the neuropsychological tests will not have access to any kind of information allowing them to identify patient assignment to treatment.

An evaluator will administer all the neuropsychological battery scales: MMSE, ADAS-Cog, NPS Battery, behavior scales NPI and CSDD and the functional scale ADCS-ADL.

The second evaluator, also on a blind basis, will administer the CDR-Sb and ADCS-CGIC. Results from previous evaluations will remain unknown for both evaluators and they must not comment any result to each other or to other study members and they will be considered blinded evaluators and will sign a document to the effect.

Anxiety and restlessness tests (during the replacement phase):

In case any sign of aggression or restlessness during the procedure, the following instruments will be used:

Measurement of overt aggression: Overt Aggression Scale (OAS)⁴⁹. This instrument measures patient aggression and provides a global score as the sum of the scores assigned to each of the different items. Increased severity is associated with higher scores.

Measurement of restlessness: Agitated Behavior Scale (ABS)⁵⁰. This includes 14 items grouped into three factors (disinhibition, and liability). The global score is obtained from the sum of the scores assigned to the different items. Increased severity is associated with higher scores.

Columbia-Suicide Severity Rating Scale (C-SSRS):

The scale is currently being used in a variety of settings from clinical trials to clinical practice. The Columbia–Suicide Severity Rating Scale (C-SSRS) was designed to quantify the severity of suicidal ideation and behaviour.

The primary outcomes to evaluate are: suicidal behaviour categorical rating, suicidal ideation categorical rating and to estimate the rate of suicidality.

We are going to use two versions of the scale that are currently being used in clinical trials:

- The **Baseline** version of the scale assesses lifetime suicidal ideation and behavior. This version is suitable as part of a patient's *first* interview in a private practice or as part of a clinical study.

- The **Since Last Visit** version of the scale assesses suicidality since the patient's last visit. This version is meant to assess patients who have completed at least one initial C-SSRS assessment, and should be used in every subsequent visit. The 'Since Last Visit' version of the C-SSRS is asking about any suicidal thoughts or behaviors the patient/participant may have had since the last time you have administered the C-SSRS.

Quality of Life AD Measure (QoL-AD):

The QoL-AD is a brief, 13-item measure designed specifically to obtain a rating of the patient's Quality of Life from both the patient and the caregiver. It was developed for individuals with dementia, based on patient, caregiver, and expert input, to maximize construct validity, and to ensure that the measure focuses on quality of life domains thought to be important in cognitively impaired older adults. It uses simple and straightforward language and responses & includes assessments of the individual's relationships with friends and family, concerns about finances, physical condition, mood, and an overall assessment of life quality.

Caregivers complete the measure as a questionnaire about their patients' QoL, while patients complete it in interview format about their own QoL. The measure consists of 13 items, rated on a four point scale, with 1 being poor and 4 being excellent. Total scores range from 13 to 52. It generally takes caregivers about 5 minutes to complete the measure about their patients; for patients, the interview takes about 10 to 15 minutes to administer. Detailed instructions for interviewer administration are available.

Scoring is straightforward - the sum of all items; patient and caregiver reports can be evaluated separately and/or combined into a single score if desired. Patients with MMSE scores of 10 or higher can usually complete it with no problem; below that caregivers can continue to complete it as proxies indefinitely.

Resource Utilization in Dementia (RUD-Lite[®]) Questionnaire:

The Resource Utilization in Dementia (RUD) Questionnaire was developed as a comprehensive tool to assess the amount of resource use among demented patients, which in a further step can be calculated into costs. It has been used in pharmaco-economical studies and it has proven to be a useful tool in the evaluation of dementia care. RUD Lite[®] has been developed as a new shorter version of the instrument RUD.

RUD assesses both formal and informal resource use of patients and the primary caregiver, making it possible to calculate costs from a societal perspective. It consists of two parts with a similar content, but the wording is adapted to a baseline situation or follow-up situation(s). The questionnaire is divided in two parts, the first one is about the patients' and the second one is about the caregivers' health status and resource use.

7.3 Method of Biochemical Marker Testing

A β in plasma, CSF and withdrawn plasma and P-tau and T-tau in CSF: These determinations will be carried out using ELISA as detailed below:

- Determination of plasma and CSF A β_{1-40} (The Genetics Company) and A β_{1-42} (Innogenetics and The Genetics Company)
- Determination of P-tau and T-tau in CSF using the Innostest P-tau and Innostest T-tau (Innogenetics)
- Determination of A β_{1-40} and A β_{1-42} pool in blood (Araclon Biotech).

- Determination of other biomarkers will be assessed from plasma removed samples.

The plasma-EDTA samples will be collected in the course of the study and will be stored frozen. The assays will be performed at the same time and in parallel with pre-treatment (baseline) samples and post-treatment samples (coded), to avoid modifications related to day variations.

7.4 Method of Neuroimaging Studies

FDG-PET

This study will be carried out according to the standard operation procedures of this study. The images will be sent to a central vendor for interpretation.

Four FDG-PET studies per patient will be made. A comparison between control and treatment groups will be performed. Qualitative and quantitative evaluation will be made by an experienced specialist.

MRI

MRI will be performed with a 1.5 Tesla magnet with a real-time acquisition system (Real-time fMRI). LX 9.1 M4 software will be used. The gradient amplitude will be 40 mT/m, with a slew rate of 150 T/m/s. A schematic representation of the process is provided.

The MRI scans will be examined by the central vendor clinical neuroradiologist, who in turn will issue a safety report for each subject. Any imaging anomaly will be communicated to the investigating team.

Once all the study MRI scans have been obtained, they will be analyzed using a visual scale with the CVHS standards, based on adequate software (3D-SPGR), including:

- Brain reconstruction in the axial plane, aligning with a standard reference image (MNT T1 matrix)
- Normal tracing of the hippocampus and of the anterior cingulate region using standard software
- Analysis of the volume of the hippocampus and of the anterior cingulate region using the LOWI system⁵¹.

Series 1 - Sagittal T1 Scout

| Plane | Mode | PSD | TE | TR | FOV | Slice/Gap | #sli | Matrix | NEX | Freq Dir | Auto Shim | Time |
|----------|------|-----|----|-----|-----|-----------------|------|-----------|-----|----------|-----------|------|
| Sagittal | 2D | SE | MF | 400 | 20 | 5/inter L50-R50 | 21 | 256 x 192 | 1 | SI | Y | 2:46 |

Series 2 – Axial T1

| Plane | Mode | PSD | TE | TR | FOV | Options | Slice/Gap | #sli | Matrix | NEX | Freq Dir | Auto Shim | Time |
|-------|------|-----|----|-----|-----|-----------|-----------|------|-----------|-----|----------|-----------|------|
| Axial | 2D | SE | MF | 400 | 20 | VBw=15.63 | 5/1 | 24 | 256 x 192 | 1 | AP | Y | 2:49 |

Series 3 – Axial fse PD

| Plane | Mode | PSD | TE | TR | ETL | FOV | Options | Slice/Gap | #sli | Matrix | NEX | Freq Dir | Auto Shim | Time |
|-------|------|-----|----|------|-----|-----|--------------|-----------|------|-----------|-----|----------|-----------|------|
| Axial | 2D | fse | 17 | 2000 | 4 | 20 | VBw=15.63 FC | 5/1 | 24 | 256 x 192 | 1 | AP | Y | 1:40 |

Series 4– Axial fse T2

| Plane | Mode | PSD | TE | TR | ETL | FOV | Options | Slice/Gap | #sli | Matrix | NEX | Freq Dir | Auto Shim | Time |
|-------|------|-----|-----|------|-----|-----|--------------|-----------|------|-----------|-----|----------|-----------|------|
| Axial | 2D | fse | 102 | 2500 | 8 | 20 | Vbw=15.63 FC | 5/1 | 24 | 256 x 192 | 1 | AP | Y | 2:10 |

Series 5 – Coronal 3D SPGR

| Plane | Mode | PSD | TE | TR | Flip | FOV | Slice | Matrix | NEX | Freq Dir | Auto Shim | Time |
|-------|------|------|----|----|------|-------------------|-------|-----------|-----|----------|-----------|------|
| Cor | 3D | SPGR | 5 | 25 | 40 | 24x18 3/4 PFOV | 124 | 256 x 192 | 1 | SI | Y | 7:44 |

Series 6 - Axial FLAIR

| Plane | Mode | PSD | TE | TR | TI | FOV | Options | Slice/Gap | #sli | Matrix | NEX | Freq Dir | Auto Shim | CV's | Time |
|-------|------|-------------|-----|-------|------|-----|---------------|-----------|------|-------------|-----|----------|-----------|------------|------|
| Ax | 2D | FLAIR ir | 156 | 10000 | 2200 | 20 | Vbw=3 1.25 | 5/1 | 24 | 256 x192 | 1 | AP | Y | Min Acq =1 | 3:20 |

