| p-Tau | Phosphorylated Tau protein |
| QoL-AD | Quality of Life Alzheimer Disease |
| RUD-Lite[®] | Resource Utilization in Dementia |
| s.c. | Subcutaneous |
| SDMT | Symbol Digit Modalities Test |
| SPECT | Single Photon Emission Computed Tomography |
| SPM | Statistical Parametric Mapping |
| ^{99m}Tc-ECD | Technetium-99m Ethyl Cysteinate Dimer |
| TGF | Transforming growth factor |
| T/m/s | Tesla per meter per second |
| T-Tau | Total Tau protein |
| UBC | United Biosource Corporation |
| ULN | Upper Limit of Normal |
| VLDL | Very Low Density Lipoprotein |
| WHO | World Health Organization |

PROTOCOL SYNOPSIS (ALBUMIN GRIFOLS + FLEBOGAMMADIF)

| | |
|--|---|
| STUDY TITLE | A multicenter, randomized, controlled study to evaluate the efficacy and safety of short-term plasma exchange followed by long-term plasmapheresis with infusion of human albumin combined with intravenous immunoglobulin in patients with mild-moderate Alzheimer's disease. |
| SPONSOR | Instituto Grifols, S.A. |
| INVESTIGATIONAL PRODUCT AND FORMULATION | Treatment Group: Albutein [®] Flebogamma [®] DIF Albutein [®] and Flebogamma [®] DIF are approved in USA. Control group: Sham procedure. |
| INDICATIONS | Probable mild to moderate Alzheimer's disease |
| OBJECTIVES | 
Primary objective
 
To evaluate the changes in the cognitive, functional, behavioral and global domains based on the different applicable psychometric batteries and scales.
 
Secondary objectives
 
 • To determine the changes in the concentration of beta-amyloid peptide in plasma and cerebrospinal fluid (CSF) in the treatment group of patients with Alzheimer's disease (AD). • To evaluate the structural changes in volume of the hippocampus, posterior cingulate area, and other associated areas based on neuroimaging studies with Magnetic Resonance Imaging (MRI) (variations versus baseline). • To determine functional brain functional changes through FDG-PET (fluorodeoxyglucose-PET). • To determine whether plasma exchange with human albumin combined with intravenous immunoglobulin (IVIG) is safe, taking into account the following factors: 
 - Type, severity and frequency of adverse reactions during and after the procedure and infusions. - Changes in vital signs and clinically relevant changes, according to the laboratory test findings. - Control of episodes of cerebrovascular accidents with MRI. |

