4.3 Planned Number of Subjects

A sample size of 312 subjects (78 per each of the 4 groups) will make it possible to detect with nearly 92% power for the first of the co-primary efficacy variable (the changes from baseline of the ADAS -Cog scores) a difference in the mean of 3 points between any of the treatment groups and the control group, assuming the common standard deviation (SD) to be 5.55 (according to the data obtained in the phase II study⁶⁵), with a level of significance of 5%. This same sample size provides over 98% power for second of the co-primary endpoint variables (the changes from baseline of the ADCS-ADL inventory scores) a difference in the mean of 6.69 points between any of the treatment groups and the control group, assuming the common standard deviation (SD) to be 10.0 (according to the data obtained in the phase II study), with a level of significance of 5%.

The study will have joint power for these co-primary endpoints of at least 90% ($0.92 \times 0.98 = 0.90$). The calculation makes the conservative assumption that these endpoints are independent. Since these endpoints may be positively correlated 90% should serve as a lower bound on power.

Assuming a global dropout rate of approximately 15%, the study would have to enroll 364 subjects to obtain 312 subjects for evaluation.

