6.1.2 Secondary Efficacy Variables

- a) Change from baseline in the cognitive, functional and neuropsychiatric scores and overall development as measured by MMSE, NPS battery, NPI, CDR-Sb, ADCS-CGIC, CSDD and C-SSRS. (6 measurements: week -3, -2 or -1 and 7-8; months 6, 9, 12 and 14) and QoL-AD, RUD-Lite[®] (5 measurements: weeks -3, -2 or -1; months 6, 9, 12 and 14). Moreover the optional questionnaires like OAS and ABS could be used at any visit in case any sign of aggression or restlessness.
- b) Variation in levels of A β ₁₋₄₀ and A β ₁₋₄₂ in CSF in the period between baseline lumbar puncture (before the start of the Intensive treatment period) and lumbar puncture immediately after the end of the last low-volume plasmapheresis (whenever this may be)
- c) Variation in the levels of A β ₁₋₄₀ and A β ₁₋₄₂ in CSF between the finalization and beginning of each of the 2 treatment periods.
- d) Levels of A β ₁₋₄₀, A β ₁₋₄₂, T-tau and P-tau in CSF throughout the study.

- e) Plasma levels of A β ₁₋₄₀ and A β ₁₋₄₂ before and after each plasma exchange for both treatment periods.
- f) Structural changes in volume of the hippocampus, posterior cingulate area, and other associated areas by MRI. Five measurements will be made (weeks -3, -2 or -1 and 7-8; months 6, 9 and 14).
- g) Variation in FDG-PET patterns (4 measurements: weeks -3, -2 or -1 and 7-8; months 9 and 14).

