7.3.2 Magnetic Resonance Imaging (MRI)

Magnetic resonance imaging data will be analyzed by MMD. The analysis will be specified in a separate SAP document.

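### Protocol 7.4 describes measuring the anterior cingulate, but the objectives and secondary variables name the posterior cingulate, for which neither document gives a method

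*Protocol*

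**What the plan says.** The structural MRI objective appears in the protocol synopsis, protocol section 2 and SAP section 2.2: "To evaluate the structural changes in volume of the hippocampus, posterior cingulate area, and other associated areas". The matching secondary variable, in the synopsis and in protocol sections 6.1.2 and 8.2, is "Structural changes in volume of the hippocampus, posterior cingulate area, and other associated areas by MRI", measured at five times: screening, weeks 7-8, and months 6, 9 and 14.

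Protocol section 7.4 sets out the method. Once every study scan is in hand, the images are to be analysed "based on adequate software (3D-SPGR), including" three steps: a reconstruction aligned to a reference image, then a tracing step, "Normal tracing of the hippocampus and of the anterior cingulate region using standard software", then a volume step, "Analysis of the volume of the hippocampus and of the anterior cingulate region using the LOWI system".

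The SAP adds no region and no model. Section 7.3.2 says: "Magnetic resonance imaging data will be analyzed by MMD. The analysis will be specified in a separate SAP document".

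**The concern.** An endpoint and the procedure that produces it should name the same structure. Here the objective and variable name one part of the cingulate, and the operative measurement steps name another. Someone who follows 7.4 literally would deliver hippocampal and anterior cingulate volumes, and would have no instruction for the posterior cingulate.

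Two things are at stake. The first is whether the trial can report the posterior cingulate component of its own secondary objective. The second is pre-specification. If the region is still unsettled when volumes are derived, it could be chosen after results are known, and a reader of the report could not tell whether the region shown was the one planned.

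**Working it through.** No formula applies, and there is no stated figure to reproduce. The check is a comparison of every place in the two documents that names a cingulate region, together with the SAP section on MRI.

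| Place | Role | Regions named |
|---|---|---|
| Protocol synopsis, objectives | Objective | Hippocampus, posterior cingulate, other associated areas |
| Protocol synopsis, secondary variables | Variable | Same |
| Protocol section 2 | Objective | Same |
| Protocol section 6.1.2 | Variable | Same |
| Protocol section 8.2 | Variable | Same |
| SAP section 2.2 | Objective | Same |
| Protocol section 7.4, tracing step | Method | Hippocampus, anterior cingulate |
| Protocol section 7.4, volume step | Method | Hippocampus, anterior cingulate |
| SAP section 7.3.2 | Analysis | None named; deferred to a separate document |

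1. **Count.** The posterior cingulate is named in six places, all of them objectives or variables. The anterior cingulate is named in one section only, in two consecutive method steps. No place names both.

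2. **Is it a slip of extraction?** This is unlikely. The word occurs twice in plain prose, in successive bullets. It is not in a broken table, a redacted gap or a description of superseded text.

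3. **Which components are affected?** The variable has three: hippocampus, posterior cingulate, and other associated areas. The hippocampus appears in both the variable and the method, so it is covered. Other associated areas are not defined anywhere, and the anterior cingulate could fall under them. The posterior cingulate has no method step. Of the two regions named specifically, therefore, one has a stated method and one does not.

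4. **Does 7.4 exclude the posterior cingulate?** No. The list of steps is introduced as a set of inclusions and is not stated to be exhaustive.

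5. **Are the data likely to exist?** Section 7.4 schedules a coronal 3D SPGR series of 124 slices and places the analysis after all scans have been obtained. Under that plan the choice of region comes after acquisition, so correcting the region need not require a new scan. The documents do not state that this series covers the posterior cingulate adequately. That is an assumption for the imaging vendor to confirm.

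6. **Does anything else depend on it?** The sample size in protocol section 4.3 (312 evaluable, 364 enrolled) is built only on ADAS-Cog and ADCS-ADL. No MRI quantity enters the power calculation or the Hochberg procedure for the co-primary endpoints.

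**The case against.** The best case against giving this much weight has four parts.

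- **The method list is open.** Section 7.4 forbids no further region. This stands, and it rules out saying that the posterior cingulate is excluded. It does not explain why the two explicit steps omit the region in the objective and specify one that no objective names.
- **The anterior cingulate may belong to the other associated areas.** This also stands as a possibility, so measuring it need not be a substitution. It still supplies no method for the posterior cingulate.
- **A separate MRI SAP exists or is planned.** It could name the posterior cingulate and be consistent with both the objective and the open list. That is a fair point, and it would settle what is analysed. Nothing in the protocol or main SAP shows that it does so, and the text of 7.4 would remain at odds with the variable until corrected.
- **The measure is supportive.** The SAP's list of secondary efficacy variables in section 7.1 has no MRI item. MRI sits under other end points in section 7.3, and the efficacy table in section 9.2.5 has no MRI row. The opening summary of protocol section 8 does not mention imaging either. This limits the weight of the point. Even so, protocol sections 6.1.2 and 8.2 list the variable as secondary efficacy, and both documents list the objective as secondary.

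**Conclusion.** The mismatch is real and should be corrected before the MRI analysis. The method section specifies the anterior cingulate in both operative steps, every objective and variable specifies the posterior cingulate, and neither document says how the posterior cingulate volume is to be obtained.

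The size is modest: one of two specifically named regions in one secondary imaging variable has no stated method at any of its five scan times. The hippocampal component, the co-primary endpoints, power and sample size are untouched.

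A reader might infer more: that the endpoint cannot be answered, that the posterior cingulate goes unmeasured in every randomised patient, or that the anterior region will be reported in its place. The documents do not support any of these. The hippocampal part is answerable as written, the list in 7.4 is not exhaustive, and the separate MRI SAP could name the posterior cingulate.

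The conclusion rests on the protocol and main SAP alone. If the separate MRI SAP already names the posterior cingulate, what remains is a wording conflict with 7.4.

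**What to change.** Change both the tracing and the volume bullets in protocol 7.4 to the posterior cingulate, or list both cingulate regions if both are wanted. Name the same region or regions in the separate MRI SAP. If the anterior cingulate is kept, say whether it counts among the other associated areas. Settle this before the unblinding described in SAP section 3 and before volumes are analysed, so that the choice cannot follow the results.

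The cost is wording in two documents and a short confirmation from the imaging vendor that the 3D SPGR series covers the posterior cingulate. If it does, no new scans are needed.
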